Non-ACT Study Protocol and Statistic Analysis Plan (SAP)

Clinical Trial Gov ID.	NCT06091982
Protocol Number	01.202308.101
Title	Renal Replacement Therapy and In-Hospital Mortality Incidence in Cardiac Surgery Associated Acute Kidney Injury
Study title	CSA AKI - RRT and Mortality Risk
Date of last Version of protocol	August 22 nd , 2023
Research question and objectives	
The purpose of this study is to evaluate the risk of patients with cardiac surgery associated acute kidney injury (CSA-AKI) with renal replacement therapy requirement RRT in related to in-hospital mortality event compared to CSA-AKI patients without the need of RRT.

Primary objective	
• To analyze the association between AKI with RRT and intra-hospital postoperative mortality in cardiac surgery patients compared with AKI patients without RRT
Secondary objectives	
• To analyze the risk of intra-hospital post-surgical mortality in cardiac surgery patients who complicated with CSA AKI• To compare the risk of intra-hospital post-surgical mortality in cardiac surgery patients who complicated with CSA AKI with requirement of RRT and without RRT• To Identify and analyze perioperative factors that play an important role in the incidence of mortality in AKI patients after cardiac surgery

Authors

1. [name], MD;
2. [name] MD;
3. [name] MD;
4. [name] MD

Department(s) and institution(s)

1. Consultant of Department of Perioperative Intensive Care and Non-Surgical Anaesthesia National Cardiovascular Centre Harapan Kita
2. Consultant of Department of Perioperative Intensive Care and Non-Surgical Anaesthesia National Cardiovascular Centre Harapan Kita
3. Consultant of Department of Perioperative Intensive Care and Non-Surgical Anaesthesia National Cardiovascular Centre Harapan Kita
4. Medical Staff of Department of Perioperative Intensive Care and Non-Surgical Anaesthesia National Cardiovascular Centre Harapan Kita

1 Table of Contents

1	Table of Contents	3
2	List of Abbreviations.....	5
3	Responsible Parties.....	7
4	Abstract	7
5	Rational and Background	8
6	Research Question and Objectives	9
6.1	Primary Objective.....	10
6.2	Secondary Objectives	10
7	Research Methods.....	10
7.1	Study Design	10
7.1.1	Design Overview	10
7.2	Setting.....	11
7.2.1	Study Population	11
7.3	Variables.....	12
7.3.1	Variables Operational Definition	13
7.4	Data Source	16
7.5	Study Size	17
7.6	Data Management.....	17

[name], MD	Address: [name] [contact] [name] Email : [contact]

Contributing Investigators

1. [name] MD Address:Department of Perioperative Intensive Care and Non-Surgical Anaesthesia
[name]
ORCID ID : [name]
2. [name] MD. Address:Department of Perioperative Intensive Care and Non-Surgical Anaesthesia
[name]
ORCID ID : [name]
3. [name] MD Address:Department of Perioperative Intensive Care and Non-Surgical Anaesthesia
[name]
ORCID ID : [name]
4. [name] MD Address:Department of Perioperative Intensive Care and Non-Surgical Anaesthesia
[name]
ORCID ID : [name]

4 Abstract

The prevalence of acute kidney injury (AKI) varies up to 30% in post-cardiac surgery patients. Of the patients who suffer from AKI, around 1 - 10% will require renal replacement therapy (RRT). Cardiac surgery associated-AKI patients who require renal replacement therapy/dialysis have higher risk of mortality. The purpose of this study was to assess the risk of AKI-RRT on intrahospital mortality, and other factors that have an association with postoperative mortality. The method was non-experimental research design as retrospective cohort analysis. Dependent variable, in-hospital mortality was determined first and then the independent variables were examined to see the relationship between the variables.

Keywords: Acute Kidney Injury (AKI), Renal Replacement Therapy (RRT), cardiac surgery, intrahospital mortality

5 Rational and Background

The overall incidence of mortality post-cardiac surgery in some literatures varies between 2-8%. Cardiac surgery associated - acute kidney injury (CSA-AKI), a common postoperative complication, has increased risk for post-operative mortality. The incidence of mortality in patients complicated with CSA-AKI is up to 60%. The most severe stage of CSA-AKI, which requires dialysis therapy, is an independent risk factor. The prevalence of acute kidney injury is ranged up to 28% in cardiac surgery patients, of which around 1 – 10% of those patients required renal replacement therapy (RRT).¹⁻⁵

The term of Acute Kidney Injury was developed by the Kidney Disease Improving Global Outcomes (KDIGO) organization in 2012, which is defined it as a sudden decrease (≤ 24 hours) in renal function characterized by an increase in serum creatinine (≥ 0.3 mg/dL or $\geq 50\%$ [1.5 times baseline]), or reduction in urine output <0.5 mL/kg/hour for >6 consecutive hours. Based on these criteria, AKI stage 3 is categorized as acute renal failure or ARF.^{1, 6, 7}

In a study conducted by Bove *et al.* in 2018, AKI is a serious complication after cardiac surgery that increases the incidence of morbidity and mortality. Renal replacement therapy (RRT) has been used as one of the important therapies in patients with severe AKI. Although the incidence of CSA-AKI requiring RRT is reported in about 1-10% of all AKI events after cardiac surgery, it is also shown that patients with severe AKI who require RRT therapy suffer a higher post-operative mortality rate. Previous studies reported intra-hospital mortality up to 43.5% in patients with AKI-RRT. Recent research found that from 412 CSA AKI-RRT patients, 174 patients (42.2%) died intra-hospital, with a EuroScore > 7 , intraoperative bleeding > 1 liter and mechanical ventilation time > 70 hours as other independent risk factors. Meanwhile, post-operative use of furosemide was considered as protective factor in this study (OR 0.48). This information is similar with the results of our previous study regarding the use of diuretics for CSA-AKI patients.⁸⁻¹¹

Considering the significant impact of AKI on the outcomes of patients' post-cardiac surgery, this study aimed to conduct an analysis of the risk factors that contribute to the incidence of post-operative mortality in patients with CSA-AKI, particularly regarding those cases in stages which required RRT. Based on the above background, this study's primary purposes was to analyze association between patients with CSA-AKI with RRT and in-hospital postoperative mortality risk compared to patients with CSA-AKI without RRT.

Study Rationale

Acute reduction in kidney function post cardiac surgery is the initial mechanism for acute kidney injury. Reduced blood flow, ischemia and reperfusion, hemolysis, activation of the inflammatory response, vascular redistribution and embolism are some of the etiologies that play an important role. The prevalence of acute kidney injury in the patient population with valve cardiac surgery is approximately 28%, with 1 – 10% requiring renal replacement therapy. Acute Kidney Injury/AKI is a strong independent predictor of post-operative mortality, particularly in patients with the requirement of renal replacement therapy. Postoperative AKI is not only increasing mortality, but also reduces long-term survival, extends the length of stay (LOS) in the intensive care unit, increases the risk of chronic kidney disease (CKD), and increases the financial burden on health facilities. Although cardiac surgery associated AKI is not a rare postoperative complication, when it reaches a severe stage that requires renal replacement therapy/RRT, the risk of postoperative mortality will increase several-fold. Apart from that, there are also other factors that increase the risk of mortality. Based on the explanation above, the formulation of the problem in this study is what is the relationship between AKI post-cardiac surgery patients with RRT on the incidence of intra-hospital mortality compared with AKI patients without RRT.

6 Research Question and Objectives

The purpose of this study is to evaluate the risk of patients with cardiac surgery associated acute kidney injury (CSA-AKI) with renal replacement therapy requirement RRT in related to in-hospital mortality event compared to CSA-AKI patients without the need of RRT.

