7.1 Study Design

This research is a non-experimental study with a retrospective cohort analysis design. Data were secondary collected from patient's registry.

The dependent variable is intra-hospital post-surgical mortality, while the independent variables are cardiac surgery patients with complication of Acute Kidney Injury (AKI) and Renal Replacement Therapy (RRT).

[figure not shown]
Analysis was carried out to determine the relationship between these variables.

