7.4 Data Source

The data to be collected in the study will be obtained from patients' registry, from electronic medical records and manual medical records. Data collection processes consist of this following process:

1. Data checking (editing)

This is an activity to check the research data form sheet for data completeness so that if there are any discrepancies it can be completed immediately by the researcher.

2. Giving code (coding)

The activity of changing data into numbers/numbers.

3. Entering data into a computer program (data entry)

This is an activity of processing data obtained from research data forms and then analyzing it by entering the data into a computer program.

4. Cleaning data (cleaning)

Data cleaning activities were carried out to check again before further analysis was carried out.

All data collected during this study must be documented on an ongoing basis in a complete, accurate, eligible, and timely fashion. The data in the eCRF should be consistent with the relevant source documents.

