7.5 Study Size

The sample size was determined based on time, namely all data on adult heart surgery patients between January 1, 2020 - December 31, 2022, who were selected based on acceptance criteria.

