7.7 Statistical Analysis Plan

All analyses will be performed on patients who underwent cardiac surgery in period between 1 January 2020 until 31 December 2022, with complication of acute kidney injury (AKI) postoperative. All data were retrieved from patient medical record retrospectively. There were no active observation or data retrieved directly from patients.

Data analysis will be carried out by the statistical team after the research samples have been taken and the data has been completed. The analysis was carried out using SPSS Version 29. and all statistical analysis plans have been completely documented in this statistical analysis plan.

Data that has been processed correctly is then analyzed by:

- a. Univariate analysis

This univariate analysis was carried out to obtain an overview of the frequency distribution of research subjects and the distribution of the proportion of cases and controls according to each independent variable (risk factor) studied.

- b. Bivariate analysis

Bivariate analysis was used to determine the relationship between the main risk factors and the incidence of death in hospital while also testing the research hypothesis using the chi square test.

c. Multivariate analysis

Multivariate analysis is carried out with the aim of describing the relationship between the dependent variable and the independent variable simultaneously in the population. Multivariate analysis was carried out by connecting several independent variables with one dependent variable simultaneously. Because the independent variables are categorical, logistic regression was used for the analysis.

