7.7.2 Statistical Methods

The statistical analyses described in this section will be performed as further outlined in the SAP, which will be finalized prior to database lock and will be included in the clinical study report for this protocol. The final SAP will take into account any amendment to the protocol.

General Statistical Methodology:

Descriptive statistics (mean, SD, median, interquartile range) will be provided for continuous variables according to the results of data normality tests. Frequencies and percentages will be presented for categorical and ordinal variables.

All analyzes will consider the security of the dataset.

Primary Outcome Analysis:

The primary outcome in this study is to look at the incidence of death in the treatment of patients who have kidney problems with CRRT or not.

Bivariate analysis was carried out using the chi square/fisher's exact test to see whether there was a difference in the incidence of death in treatment between groups (CRRT vs Non-CRRT)

which was then continued to the multivariate analysis stage if it had a p value <0.25 , multivariate analysis was carried out using regression multiple logistics with a significance level of 0.05 which shows that it is a variable that influences the incidence of death in care.

Secondary Endpoint Analysis:

The secondary outcome in this study is to look at the factors causing CRRT in patients undergoing cardiac surgery with AKI.

Bivariate analysis was carried out using the chi square/ Fisher's exact test to see whether there were differences in patient characteristics between patients who were given CRRT and those who were not, which was then continued to the multivariate analysis stage if it had a p value <0.25 . Multivariate analysis was carried out using multiple logistic regression with The significance level is 0.05 which shows that it is a variable that influences the incidence of CRRT use.

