8.3 Subject Identification and Privacy

A unique subject number will be assigned to each subject at inclusion. This number will serve as the subject's identifier in the study as well in the study database. The Investigator must ensure that the subjects' anonymity is maintained.

The Investigator should keep a separate log of subjects' identification numbers, names, addresses, telephone numbers and hospital numbers (if applicable). Only authorized persons will have access to identifiable personal details, if required for data verification. The Investigator is responsible for retrieving information from personal medical records. Data protection and privacy regulations will be observed in capturing, forwarding, processing, and storing subject data.

9 Management and Reporting of Adverse Events

This study design is retrospective study. All the events and incidences were already happened in the past period. This study does not interact directly to patients, there are no adverse events were caused directly by the study.

10 Plans for Disseminating and Communicating Study Results

After completion of the study, we shall prepare a final report of study results, in close collaboration with the coordinating Investigator. All publications and presentations should be based on the final study report.

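### The abstract determines death before the risk factors and no masking is described, so loosely defined pre-operative history items could be recorded differently by outcome and emerge as false mortality factors

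*Combined protocol and SAP*

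**What the plan says.** The declared design is a cohort. Section 7.1: "This research is a non-experimental study with a retrospective cohort analysis design". Section 7.5 takes every eligible patient in a calendar window, "namely all data on adult heart surgery patients between January 1, 2020 - December 31, 2022", and Section 7.2.1 selects on AKI after surgery, not on death.

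Two places describe work that starts from the outcome. The abstract (Section 4), directly after naming the cohort design, says: "Dependent variable, in-hospital mortality was determined first and then the independent variables were examined to see the relationship between the variables". Section 7.7(a) plans to tabulate the "distribution of the proportion of cases and controls according to each independent variable".

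On who handles the charts, Section 8.3 says: "The Investigator is responsible for retrieving information from personal medical records". For incomplete forms, Section 7.4 says that "if there are any discrepancies it can be completed immediately by the researcher". Neither section, nor any other, describes masking to death, coding rules for the history items, duplicate abstraction or a log of edits. Section 7.8 admits limited cross-checking but does not name outcome-dependent recording.

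On timing, Section 7.7 says the analysis plans are already fully documented, while Section 7.7.2 refers to a SAP "which will be finalized prior to database lock".

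**The concern.** In a cohort, exposures and covariates are fixed first and the outcome is attached afterwards. The abstract gives the reverse order. A person who knows that a patient died may look harder for a history of stroke or kidney disease, or fill a gap differently. Such error depends on the outcome, so it can create an association with death where none exists; it does not only dilute a real one.

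The items most open to this are the histories in Table 7.2. Smoking and renal disease have no definition beyond what the notes say. Stroke is any recorded diagnosis. Diabetes rests on history plus blood sugar results with no threshold. Hypertension has blood pressure limits but is still taken from the recorded history. These items feed the secondary objective on perioperative factors in mortality (Section 6.2), through the p < 0.25 screen and the logistic model in Section 7.7.2.

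**Working it through.** The plan gives no recording-error rate, sample size or death count, so there is no figure of its own to reproduce. The numbers below are illustrations on assumed inputs.

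**1. Apparent odds ratio for an item with no true link to death.** Let p be the true prevalence, Se the share of true carriers recorded, and FP the share of non-carriers wrongly recorded. The recorded proportion in each outcome group is

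r = p × Se + (1 − p) × FP

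and the apparent odds ratio is [r_d / (1 − r_d)] / [r_s / (1 − r_s)], with d for deaths and s for survivors. With p = 0.15 (assumed):

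| Se deaths / survivors | FP deaths / survivors | r_d | r_s | Apparent OR |
|---|---|---|---|---|
| 95% / 85% | 0 / 0 | 0.1425 | 0.1275 | 1.14 |
| 95% / 75% | 0 / 0 | 0.1425 | 0.1125 | 1.31 |
| 95% / 85% | 3% / 1% | 0.1680 | 0.1360 | 1.28 |
| 95% / 75% | 5% / 1% | 0.1850 | 0.1210 | 1.65 |

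For the last row: (0.185 / 0.815) / (0.121 / 0.879) = 0.2270 / 0.1377 = 1.65. With equal Se and FP in the two groups the ratio is 1.00. Swapping the rates between deaths and survivors gives the reciprocal, so the direction is an assumption too.

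**2. Chance that such an item passes the plan's thresholds.** Assumed: 300 to 1,000 patients, mortality 10% to 40%, prevalence 20% to 40%, sensitivity 70% in survivors, no false positives. The method is the normal approximation for two proportions, unadjusted and two-sided, counting only the tail in the direction of the bias.

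| Se in deaths | Apparent OR | Chance of p < 0.25 | Chance of p < 0.05 |
|---|---|---|---|
| 80% | 1.17 to 1.21 | 21% to 58% | 6% to 28% |
| 90% | 1.35 to 1.45 | 30% to 93% | 10% to 76% |

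Middle case: 600 patients, 20% mortality (120 deaths, 480 survivors), prevalence 40%, sensitivity 90% against 70%. The recorded proportions are 0.4 × 0.9 = 0.36 and 0.4 × 0.7 = 0.28. The odds ratio is (0.36 / 0.64) / (0.28 / 0.72) = 1.45. The item passes the screen in 71% of studies and reaches p < 0.05 in 41%. With equal recording, the matching one-tail rates are half the nominal ones: 12.5% and 2.5%.

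**3. Which variables are exposed.** RRT and IABP use, ventilation beyond 48 hours, ICU days, age and the last pre-operative creatinine are device, time or laboratory records made during care. Knowing the outcome leaves little room to code them differently. The scope is therefore the five history items and gaps in the form that are filled later.

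**The case against.** The strongest reply is that nowhere do the documents say that the coder knows who died. Section 7.1 also names the dependent variable and then the independent ones, so the abstract's sentence may mean only that the outcome was specified first. Data are also described as collected secondarily from a registry, so some items may have been recorded before this study began. Figure 7.1 could not be read here and may show a workflow. This stands in part. Outcome-aware coding is the natural reading of the abstract's sentence but remains an inference. Under either reading, the sentence needs rewriting and the safeguard is missing.

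A reader might also infer stronger things that the documents do not support:

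- *That this is a case-control study.* All eligible patients enter regardless of death. The wording in 7.7(a) is inconsistent with that but does not itself cause information bias.
- *That mortality by RRT group goes unreported.* Section 7.7.2 plans a test of death between the CRRT and non-CRRT groups.
- *That one person abstracts the charts and settles the discrepancies.* Section 7.4 says only that a researcher completes them, and the sentence in 8.3 sits in a privacy section.
- *That cut-points and covariates are free to be chosen after the deaths are seen.* Most cut-points and the candidate covariates are already written in 7.3 and Table 7.2, with the entry rule in 7.7.2. Finalising before lock does not mean that anyone has seen results. What remains is the mismatch between 7.7 and 7.7.2 on whether the plan is final.

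Finally, blinding has limits. RRT is defined up to discharge, so coding it usually reveals whether the patient died. That is correct, and it confines the remedy to the pre-operative items.

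**Conclusion.** The concern holds as a risk that the plan leaves open; bias is not demonstrated. The abstract states an outcome-first order, 7.7(a) echoes it, both conflict with the all-eligible cohort, and no masking is described. If the order is followed literally, outcome-dependent recording of the pre-operative history items could produce false mortality factors for the secondary objective.

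The size is unknown. The range of about 1.1 to 1.7 for a null item rests wholly on assumed prevalence and error rates, and the documents say nothing on whether recording differs by outcome, by how much, or in which direction. The pass rates are unadjusted and do not describe the multivariable result.

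A reader might infer that the primary result is compromised. The documents do not support that: RRT use is an objective record and the groups are compared by exposure. Mis-recorded covariates could reach the adjusted RRT estimate only indirectly, which is not quantified here. This is a worthwhile low-cost improvement, not a defect that invalidates the study.

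**What to change.** - **Abstract:** rewrite the sentence in cohort order: identify the patients with AKI, record RRT and the other variables, then relate them to in-hospital death.
- **Section 7.4:** take the pre-operative items from pre-operative notes, and close those fields before the post-operative course and discharge status are read. Log any later edit.
- **Section 7.7(a):** replace the case/control wording with RRT and no-RRT groups.
- **Section 7.7.2:** state that this version is the final SAP before death is linked, and that later changes are labelled post hoc. This also removes the mismatch with 7.7.
- **Section 7.8:** if abstraction is already complete, name outcome-dependent recording of the history items as a limitation. The surgery window closed in December 2022 and the protocol is dated August 2023, so this may apply; the documents do not say.

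The cost is some rewording and a two-step pass through the charts, with the same staff and records. Protection is partial: RRT, ventilation and ICU stay cannot realistically be coded blind to death, and abstractors may still recognise some patients who died.
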